For those patients in the Cyclosporine arm, **Cyclosporine trough level measurements will be done every 2 weeks +/- 3 days after initiation of Cyclosporine until levels are stable and at target. Potassium and creatinine will also be checked in conjunction with CSA level. If Cyclosporine dose is changed during treatment, potassium, creatinine and CSA level will be rechecked every 2 weeks +/- 3 days until levels are stable and at target.** Cyclosporine levels will also be assessed whenever serum creatinine rises by $>30\%$ without a recognizable reason such as volume depletion, additional drugs, sepsis, etc. Patients who cannot tolerate the medications and/or who are treatment failures at 6 months will exit the study at 6 months (i.e., the 6 month visit and accompanying data collection should still occur). Patients who go in to complete remission will discontinue study drug but will continue with full visit follow-ups until month 24 as scheduled. However, the therapeutic/management plan for these patients will be solely at the discretion of the managing nephrologist although while in CR no further immunosuppressive therapy is recommended. Likewise, patients who relapse from either a partial or complete remission or who are not in partial or complete remission by the end of the treatment period (i.e., 12 months) will continue with the visit schedule, but the therapeutic/management plan will be solely at the discretion of the managing nephrologist. Finally, for patients who temporarily stop taking Cyclosporine, there are three possible scenarios:

1. Patients who discontinue Cyclosporine for < 2 weeks may simply be restarted on the study drug and continue to fully participate in the trial. The treatment is to be restarted at its former dose and the patient returned to the regularly scheduled follow-ups including the periodic sampling for assessing potassium, creatinine and CSA trough levels.
2. Patients who discontinue Cyclosporine for ≥ 2 weeks, but < 4 weeks may also be restarted on the study drug at its former dose and fully participate in the trial, but the temporary discontinuance will be logged as a protocol deviation and the missed treatment days will be made up at the end of month 12. This is to ensure that all patients receive approximately 12 months of treatment with study drug.

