In all patients, CBC with differential, serum creatinine, electrolytes, albumin, urinalysis, 24-hour Uprot/Ucrea ratio, and creatinine clearance will be evaluated as noted in Tables 2a and 2b. In patients receiving RTX, additional tests will include: quantification of lymphocyte subsets by flow cytometry, serum immunoglobulin levels, and determination of humanized anti-chimeric antibodies (HACA) at study visits Day 1, 6 months, and 9 months. HACA will be performed free of charge by Genentech using established techniques.

Anti-PLA2R Assay

Recent evidence suggests that the presence of auto-antibodies to the M-type phospholipase A2 receptor (PLA2R) is a specific marker of idiopathic MN, found in greater than 70% of patients.⁷⁶ When the analysis is limited to new-onset, nephrotic patients with idiopathic MN, this sensitivity increases further. The presence of anti-PLA2R correlates well with disease activity, disappearing with a spontaneous or treatment-induced remission, and reappearing with a relapse of MN.

We intend to explore the correlation of anti-PLA2R and disease activity by carefully looking at anti-PLA2R titer in response to RTX/CSA and the achievement of partial or complete remission. In those patients that have no remission from their disease in response to RTX/CSA, we will determine if circulating anti-PLA2R is still present which might suggest the need for a second course of RTX, continued treatment with CSA, or alternate immunosuppressive therapy. Furthermore, in those patients that are in complete remission at 6 months, partial or complete remission at 12 months, , or have a $\geq 50\%$ reduction in proteinuria from baseline by 12 months (i.e., the MENTOR remission cohort), we intend to explore the following critically important questions:

1. The relationship between the rate of increase of anti-PLA2R titer and patient relapse
2. The relationship between the absolute change in anti-PLA2R titer (from baseline/remission point) and clinical phenotype (i.e., response/relapse time)

3. The predictive capacity of changes in anti-PLA2R titer with regard to relapse and/or durability of remission
4. The timing between changes in anti-PLA2R titer and any subsequent clinical relapse

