Tests/Assessments	Screen	T0	Day 15	Day 28	Day 90/3m	Day 180/6m	Day 210/7m	Day 240/8m	Day 270/9m	Day 300/10m	Day 330/11m	Day 365/12m	Day 395/13m	Day 425/14m	Day 455/15m	Day 485/16m	Day 515/17m	Day 545/18m	Day 605/20m	Day 665/22m	Day 730/24m	Day 790/26m	Day 850/28m	Day 910/30m	Day 970/32m	Day 1030/34m	Day 1095/36m		
Randomization		X																											
History/Exam	X	X			X	X			X			X							X			X							
CBC with differential	X	X			X	X			X			X							X			X							
BUN, Cr, Lyses, Albumin (including potassium)	X	X			X	X			X			X							X			X							
CPK			X		X																								
CSA level †			X	X	X	X			X			X																	
Lipid panel		X				X						X										X							
Serum Pregnancy	X	X				X																							
Anti-PLA2R antibodies	X	X			X	X	X ^d	X ^d	X	X ^d	X ^d	X	X ^c	X ^{c,d}	X ^c	X ^{c,d}	X ^c	X	X ^{c,d}	X	X ^{c,d}								
DNA sample		X																											
Gene Expression		X										X										X							
Potassium and Cr ₁			X	X																									
UA	X	X				X						X										X							
Uprot/Ucrea 24h	X	XX			X	XX			X			XX							XX			XX							
Uprot/Ucrea (spot urine)							X ^d	X ^d		X ^d	X ^d		X ^c	X ^{c,d}	X ^c	X ^{c,d}	X ^c		X ^{c,d}	X ^{c,d}		X ^{c,d}							
24h creatinine for CrCl	X	X				X						X										X							
24h urine urea		X				X						X										X							
24h urinary Na ⁺		X				X						X										X							
Quality of life-KDQOL		X				X						X										X							
Adverse Events			X	X	X	X			X			X		X				X			X								
Dispense/Return Medication		X	X	X	X	X			X ^a			X ^a	X ^a	X ^{a,b}															

1. Potassium, Cr checked at 2 weeks +/- 3 days post Cyclosporine initiation. If Cyclosporine is increased or decreased during treatment, potassium, Cr and CSA will be rechecked after 2 weeks +/- 3 days

†Patient will have blood levels of CSA monitored every 2 weeks +/- 3 days until target is reached and then as per above schedule.

^aOnly for participants who continue on CSA at 6 months

^bTelephone or in-clinic visit to confirm successful down-titration of CSA for patients who continue on medication to 12 months (if by phone, medication should be returned at 18 month visit)

^c For participants in the MENTOR remission cohort who are in PR or CR at 12 months or have a $\geq 50\%$ reduction in proteinuria from baseline by 12 months

^d For participants in the MENTOR remission cohort who are in CR at 6 months

Table 2b: Test Schedule and Monitoring for Rituximab Treatment Arm

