Sample size estimation: The primary study goal is to compare the long-term efficacy of RTX (given at baseline and repeated at 6 months) with CSA (12 months treatment + 2 months taper) using proteinuria response 24 months after randomization. Proteinuria positive response will be defined as attaining and maintaining CR or PR at 24 months after randomization. We propose to establish that the RTX treatment is non-inferior to the CSA. RTX will be considered non-inferior to CSA if the response rate of the RTX arm is at most 15% worse than that of CSA arm. In addition we will compare the quality of life (QOL) and adverse event (AE) profile over the course of the treatment period. The preliminary data has indicated that CSA is effective in inducing a CR/PR of proteinuria in between 60 and 75% of MN cases.^{48, 51} However, nephrotic syndrome (NS) relapses may be as high as 50% once CSA is discontinued.⁸⁵ Thus, we estimate a CR/PR rate in patients treated with CSA of 30-50% at 24 months after randomization.⁸⁵ Similar remission and relapse rates with the use of Tacrolimus (another calcineurin inhibitor) have been reported by Praga et al.⁵⁶ In this latter study, almost half of the MN patients had a relapse of the nephrotic syndrome after tacrolimus was discontinued.⁵⁶ On the other hand, based on the long term follow up on the 35 patients treated with RTX from our 2 studies, we estimate the relapse rate to be <10% at 24 months.^{71, 75} We observed a CR/PR rate at 12 months, very similar to the rate for calcineurin inhibitors i.e. 60%, and in our second study completed recently, we observed an 80% CR/PR rate at 24 months, implying that RTX had a ~20% failure rate with 95% (CI 6% to 44%). To be conservative for the sample size estimation, we considered a maintained CR/PR rate at the low end of our previous experience, 55% CR/PR for RTX at 24 months and at the high end of our experience with CSA (CNI therapy) CR/PR for CSA of 45%. We propose a non-inferiority trial with non-inferiority margin $\delta = 15\%$, with the null hypothesis of $\pi_{RTX} - \pi_{cyclosporine} < \delta$, where π_{RTX} and $\pi_{cyclosporine}$ are the proportions of patients with CR/PR at 24 months in treatment arms of RTX and CSA, respectively. Under these assumptions, and a one sided alpha of 0.025, enrollment of 63 evaluable patients per study arm is required to achieve 80% power to show that the RTX is not inferior. For the intent to treat (ITT) analysis we will consider all patients lost to follow up to be non-responders so no correction to the sample size is needed for dropouts. With 63 patients per arm we will have 80% power to detect moderate differences of .6 standard deviations for continuous measures or around .25 for proportions for the comparisons of the QOL and AEs.

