
Statistical and Analytical Plan: All demographics and entry laboratory data will be summarized by treatment group. Frequency distributions will be used to describe categorical values and basic summary statistics (mean, standard deviation, median, and inter-quartile range) will be used to describe continuous values. To provide more reliable estimates and minimize the “regression to the mean effect” duplicate urine measurements obtained at baseline (Time 0), 6, 12, 18 and 24 months will be averaged. The chi-square test and logistic regression will also be used to compare the percent of patients with remission at 6, 12, 18, and 24 months adjusting for treatment center and the baseline

proteinuria (UP<8g/24h vs >=8g/24h). Odds ratios and associated 95% confidence intervals will be estimated. The formal test for the primary endpoint will be based on the significance of the treatment group factor in the logistic regression model for UP failure at month 24. The Wilcoxon rank-sum test and ordinal logistic regression will be used to compare the ordered remission status outcome (1=CR, 2=PR, 3=NR) between treatment groups. Longitudinal methods for categorical outcomes (e.g. generalized estimating equation or GEE models) will be used to compare remission status profiles between treatment arms. Unless otherwise noted, all tests will be two-sided with alpha level 0.05.

For repeated measures such as urine protein, individual rates of change will be estimated using within-patient linear regression analyses (including data from all visits). Because of the non-linearity of the changes in proteinuria log transformation estimates will be used. Renal function readings will be censored at initiation of dialysis or renal transplant. Additionally, mixed effects models, assuming a random center effect, and a random slope of creatinine clearance and/or reciprocal of creatinine and intercept for each patient will be fit using data from all visits. These models allow comparison of the average slope between groups, while taking into account that each patient's slope may be based on a variable number of readings. Treatment group comparisons regarding quality-of-life scales will be done using repeated measures analyses and mixed effects models.

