Adverse events (both patient and event counts) will be tabulated by body system, severity and, for each severity, by investigator-assessed relationship to study drug. Group comparisons for adverse events with 4 or more occurrences will be done using chi-square or Fisher's exact test. The last RTX injection is at 6 months and the tapering of Cyclosporine will be completed by the end of month 14. Hence, the adverse events analyses will focus on events through month 18, allowing these additional months for potential lingering Cyclosporine or RTX complications.

The analysis of the primary endpoint (urine protein failure at month 24) will be intent-to-treat (ITT), and will include all randomized subjects in the analysis. For those without a 24 month visit, the 18 month visit results will be used if available, otherwise they will be assumed to have failed at 24 months. Per protocol (PP) analyses will also be done including only those subjects who receive a full course of study medication and who have a 24 month visit.

Interim analyses: No interim analyses for efficacy will be performed during the trial, however safety data will be compiled and reviewed approximately every six months or at the request of the Data and Safety Monitoring Board.

Investigator and Coordinator Training: In order to make efficient use of funding, annual investigator and coordinator meetings will be coordinated with national nephrology meetings where possible. It is expected that the majority of the training will occur through web-based technology and will be coordinated through the data management and coordinating Center.

The **Data Management and Coordinating Center (DMCC)** is located at the Applied Health Research Center (AHRC) at St. Michael's Hospital/University of Toronto. The DMCC will be responsible for facilitating all aspects of the study planning, training, implementation, data collection and analysis.

The clinical information collected for this study will be stored at the DMCC at the Applied Health Research Centre of St. Michael's Hospital in Toronto, ON, Canada and also sent to a federal data repository held by the Office of Rare Diseases Research (ORDR) and located at the University of South Florida (USF) in Tampa, FL.

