An unexpected adverse event is defined as any adverse experience...the specificity or severity of which is not consistent with the risks of information described in the protocol or product monograph.

Expected adverse events are those that are identified in the research protocol or product monograph as having been previously associated with or having the potential to arise as a consequence of participation in the study.

All adverse events that occur between Time 0 and study termination will be reported. All reported adverse events will be classified using the current version of the Common Terminology Criteria for Adverse Events (CTCAE) developed and maintained by CTEP at National Cancer Institute.

- Within **24 hours** (of learning of the event), investigators must report any Serious Adverse Event (SAE) that:
 - Is considered life-threatening/disabling or results in death of subject
 - OR-
 - Is Unexpected/Unanticipated
- Investigators must report all other SAEs within **5 working days** (of learning of the event).
- All other AEs must be reported to the DMCC within **20 working days** of the notification of the event or of the site becoming aware of the event.

Local institutional reporting requirements to IRBs, any GCRC oversight committee and the FDA, if appropriate, remain the responsibility of the treating physician.

As part of the reporting structure, SAEs will be reported to Health Canada, Genentech Drug Safety and the Genentech medical science liaison. An adverse event summary form will be completed and will be summarized for each IRB and Health Canada annually.

Sites will enter all Adverse Event data into the study eCRF. Upon entry of a serious adverse event, the system will notify the DMCC by email. The DMCC will in turn notify the study PIs, the designated medical monitor and any other designated personnel by email. The medical monitor will then review the SAE data to determine causality (definitely not related, probably not related, possibly related, probably related, definitely

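### Adverse events are tested between arms although some laboratory tests are run more often, or only, in one arm, so differences in laboratory-detected events can come partly or wholly from testing

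*Combined protocol and SAP*

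**What the plan says.** All places are in the combined protocol and SAP.

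- **Test.** Statistical and Analytical Plan: "Group comparisons for adverse events with 4 or more occurrences will be done using chi-square or Fisher's exact test". The window is set by "Hence, the adverse events analyses will focus on events through month 18" and the level by "Unless otherwise noted, all tests will be two-sided with alpha level 0.05".
- **Shared chemistry.** Tables 2a and 2b both schedule creatinine and electrolytes at months 3, 6, 9, 12 and 18.
- **Extra tests on CSA.** Table 2a adds a potassium and creatinine row at Days 15 and 28, with the footnote "Potassium, Cr checked at 2 weeks +/- 3 days post Cyclosporine initiation". Patient monitoring and evaluation ties both to the two-weekly CSA level until it is stable and at target, and adds: "If Cyclosporine dose is changed during treatment, potassium, creatinine and CSA level will be rechecked every 2 weeks". Table 2b has no such row. CPK stands in Table 2a (Day 15 and Day 90) and not in Table 2b.
- **Extra tests on RTX.** Laboratory testing: "In patients receiving RTX, additional tests will include: quantification of lymphocyte subsets by flow cytometry, serum immunoglobulin levels". Table 2b has rows for these; Table 2a has none.
- **What counts as an event.** Adverse event reporting requires all adverse events from Time 0 to be reported and classified by CTCAE. It does not say when a laboratory value becomes an adverse event.

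**The concern.** An abnormality that comes and goes is found more often the more often one looks. Both arms carry background risk: both receive maximised angiotensin blockade, for which the run-in section names hyperkalaemia as a side effect, and both receive a statin. The abnormalities are looked for unequally. On CSA the process also feeds itself, since a creatinine rise leads to a dose change and a dose change leads to more tests.

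Aim 4 is that RTX has the better side-effect profile, and adverse events are a secondary endpoint. Extra potassium, creatinine and CPK testing pushes the comparison towards that aim; immunoglobulin testing pushes against it. In neither case does the planned test separate toxicity from detection.

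**Working it through.** **The plan's own figure first.** Sample size estimation states "enrollment of 63 evaluable patients per study arm is required to achieve 80% power" for the primary comparison, and about 80% power for a difference of around 0.25 in adverse event proportions. The non-inferiority formula with 45% against 55%, margin 15% and one-sided 0.025 returns 63 per arm. A two-sided 0.05 comparison of 0.375 with 0.625 at 63 per arm has power 0.809. Both figures reproduce.

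**Inputs from the documents.** 63 per arm; two-sided 0.05; only events with a total of at least 4 are tested; k = 5 post-baseline tests on RTX; k = 7 on CSA (the same 5 plus Days 15 and 28), read from the extracted tables.

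**Assumptions.** The chance q of an abnormal result per test is the same in both arms; the documents give no value, so 1%, 2% and 5% are shown. Occurrences are counted as patients affected. The plan does not say when chi-square and when Fisher applies; here chi-square is used if the smallest expected count is at least 5, otherwise Fisher.

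**Step 1: independent tests.** The chance of at least one finding is 1 − (1 − q)^k. At q = 5% this is 1 − 0.95^5 = 22.6% on RTX and 1 − 0.95^7 = 30.2% on CSA. Summing the two binomial distributions over all tables that reject gives the false-positive rate:

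| q | RTX, 5 tests | CSA, 7 tests | False-positive rate | Fisher throughout |
|---|---|---|---|---|
| 1% | 4.9% | 6.8% | 3.9% | 2.4% |
| 2% | 9.6% | 13.2% | 9.2% | 5.5% |
| 5% | 22.6% | 30.2% | 16.1% | 11.9% |

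With 5 tests in both arms the rate is about 5% or below.

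**Step 2: more rechecks.** If every CSA patient had 9 or 11 tests, the rates would be 42% and 70% at q = 5%, and 21% and 37% at q = 2%. These counts are illustrations; the documents give no average number of rechecks.

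**Step 3: correlated tests.** Repeat results in one patient are unlikely to be independent. With a beta-binomial model of correlation ρ, set a = q(1 − ρ)/ρ and b = (1 − q)(1 − ρ)/ρ; the chance of no finding in k tests is the product of (b + i)/(a + b + i) for i = 0 to k − 1. At q = 5%:

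| ρ | 7 v 5 tests | 9 v 5 | 11 v 5 |
|---|---|---|---|
| 0.1 | 10% | 22% | 37% |
| 0.3 | 6% | 10% | 14% |
| 0.5 | 5% | 7% | 8% |

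At q = 2% and ρ = 0.3 the rates are 4%, 5% and 7%.

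**Step 4: tests in one arm only.** Suppose the untested arm records none. Four patients against none, the smallest total that is tested, gives chi-square = 126 × (4 × 63)² / (4 × 122 × 63 × 63) = 4.13, p = 0.042; Fisher gives p = 0.119. Six against none gives Fisher p = 0.028. If the tested arm shows the finding in 5%, 10% or 15% of patients, the result is significant in 9%, 61% or 93% of trials under the same test rule.

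**The case against.** Five points can be made for the plan.

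- **A real effect is expected.** A reader might infer that any difference in these events is produced by testing alone. The documents do not support that: the section on cyclosporine toxicity describes an acute effect on filtration, and the blood-pressure section expects hyperkalaemia to be worse on CSA. This stands. Testing can produce a difference; it need not be the whole of it. But the planned test cannot tell the two apart.
- **The large rates rest on strong assumptions.** A reader might take 42% or 70% as the expected error. They need independent tests and 9 or 11 tests in every CSA patient, whereas rechecks apply only until target or after a dose change. This stands, and the scheduled minimum is the firmer basis.
- **Not every abnormal value is an adverse event.** The definition speaks of an unfavourable and unintended sign, symptom or disease, and B-cell depletion is what RTX is meant to do. This stands in part. However, the list of stopping points names persistent rises in liver enzymes, potassium and creatinine and then refers to other adverse effects, so such findings are plainly treated as adverse.
- **CK may be checked on RTX too.** The statin rule under Concomitant Treatment mentions high CK without naming an arm. CPK is therefore one-arm by schedule, not by prohibition, and the RTX count need not be zero.
- **Renal function has its own analysis.** Slopes are modelled with allowance for a variable number of readings, and central creatinine is collected at common times. True, but this does not change the adverse event test and does not cover potassium, CPK or immunoglobulins.

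**Conclusion.** The point holds in a bounded form. The unequal testing is written into the schedules, the between-arm test covers all adverse events with 4 or more occurrences, and no safeguard is stated. For potassium and creatinine at 7 against 5 tests, the false-positive rate is about 4–16% for q = 1–5% if tests are independent, and about 5–10% at q = 5% with correlation 0.1–0.5. At q = 1% there is no excess over 5%. Rechecks increase it by an amount the documents do not allow one to fix. The one-arm tests are the clearer problem: a 10% finding rate is significant in about 61% of trials with no comparison made under equal conditions. All of this takes q, the correlation, the recheck counts and the 10% as assumptions, and requires that sites report the laboratory findings as adverse events. It affects a secondary safety comparison and the reading of Aim 4, not the primary endpoint. It should be corrected because the correction is cheap.

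**What to change.** Amend the adverse event paragraph of the Statistical and Analytical Plan in two ways.

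1. Report events detected only by tests scheduled in one arm (CPK, immunoglobulins, lymphocyte subsets) descriptively by arm, without a between-arm p-value.
2. Keep the all-event comparison. For laboratory-defined events tested in both arms (potassium, creatinine), add a between-arm analysis that uses only results from the shared post-baseline visits (months 3, 6, 9, 12 and 18; not Time 0) with the same CTCAE cut-offs. State that a difference seen only in the all-event comparison is not to be read as drug toxicity without noting the unequal testing.

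The paragraph should also say when a laboratory value counts as an adverse event.

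The cost is wording and a little more analysis. The shared-visit analysis may miss early, transient CSA effects, because Day 15, Day 28 and dose-change results drop out of it. It must therefore stand beside the all-event comparison and not replace it; those events stay visible there and in the safety listing. The monitoring schedule does not change.
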